2.5.4 Supportive analyses

Not applicable.

2.6 Analysis of the key secondary objective

Not applicable.

2.7 Analysis of secondary efficacy objective(s)

2.7.1 Secondary endpoints

2.7.1.1 Phase Ib part

Overall response rate (ORR), Progressive Free Survival (PFS), Clinical Benefit Rate (CBR), Duration of Response (DOR), Disease Control Rate (DCR) per RECIST v1.1 and per immune related Response Criteria (irRC), and Overall Survival (OS).

2.7.1.2 Phase II part

For Group 1, 3 and 4: ORR per irRC, PFS, DOR, DCR, CBR per RECIST v1.1 and per irRC, and OS.

For Group 2: CBR per irRC, PFS, DOR, DCR, ORR per RECIST v1.1 and per irRC, and OS.

2.7.2 Statistical hypothesis, model, and method of analysis

Tumor response will be determined per local investigators' assessment, according to RECIST v1.1 and irRC. For the purpose of this study, Clinical benefit rate (CBR) is defined as the

proportion of patients with a best overall response of CR or PR, or an overall lesion response of SD which lasts for a minimum time duration of 16 weeks (4 months).

For all efficacy parameters, data will be listed, summarized, or analyzed by treatment group for the phase Ib part, and by disease group (groups 1 to 4) for phase II patients treated at the MTD/RP2D.

Bayesian analysis described in [Section 2.5.2.2](#) will be performed and reported based on response data per irRC.

ORR, CBR and DCR will be summarized with accompanying 90% confidence intervals.

PFS, along with DOR for patients who experience a CR or PR at any time on study will be listed by patient. PFS will be analyzed using Kaplan-Meier estimates (including graphical representation) with 90% CIs of median survival for each treatment group/disease group.

OS data will be listed for all patients enrolled in the Phase Ib and Phase II parts. Descriptive statistics for OS endpoint (e.g., median OS and 90% CI of the Kaplan-Meier estimates) will be provided if applicable by treatment group and furthermore by disease group for patients treated at the MTD/RP2D in the Phase II part.

Individual lesion measurements and overall response assessments will be listed by patient and assessment date. Best overall response per RECIST v1.1 and per irRC will be listed and tabulated.

2.7.3 Handling of missing values/censoring/discontinuations

Patients in the phase II part who have BOR of unknown (UNK) or not assessed (NA) will be considered as a treatment failure in the secondary analysis of ORR according to irRC.

For the analysis of PFS, patients without documented disease progression or death are censored at the time of last valid tumor assessment documenting non-progression (one of complete response, partial response, or stable disease). Patients without any valid post-baseline tumor assessment response (one of CR, PR, SD, or PD) will be censored on the start date of treatment. Patients who have a PFS event (progression or death) after two or more consecutive missing assessments from the last valid tumor assessment will be censored on the last valid tumor assessment (or on the start date of treatment among those with only one valid postbaseline tumor assessment).

Other missing data will simply be noted as missing on appropriate tables/listing.

If any alternative cancer therapy is taken while on study any subsequent efficacy assessments would be excluded from all relevant efficacy summary.

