14.1.3.2 Time to event variables

14.1.3.2.1 Progression-free survival

Usually in all Oncology studies, patients are followed for tumor progression after discontinuation of study medication for reasons other than progression or death. If this is not used, e.g. in Phase I or II studies, this should be clearly stated in the protocol. Note that randomized trials (preferably blinded) are recommended where PFS is to be the primary endpoint.

Progression-free survival (PFS) is the time from date of randomization/start of treatment to the date of event defined as the first documented progression or death due to any cause. If a patient has not had an event, progression-free survival is censored at the date of last adequate tumor assessment.

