14.1.3.2.7 Definition of start and end dates for time to event variables

Assessment date

For each assessment (i.e. evaluation number), the **assessment date** is calculated as the latest of all measurement dates (e.g. X-ray, CT-scan) if the overall lesion response at that assessment is CR/PR/SD/UNK. Otherwise - if overall lesion response is progression - the assessment date is calculated as the earliest date of all measurement dates at that evaluation number.

Start dates

For all “time to event” variables, other than duration of response, the randomization/ date of treatment start will be used as the start date.

For the calculation of duration of response the following start date should be used:

- Date of first documented response is the assessment date of the first overall lesion response of CR (for duration of overall complete response) or CR / PR (for duration of overall response) respectively, when this status is later confirmed.

End dates

The end dates which are used to calculate ‘time to event’ variables are defined as follows:

- Date of death (during treatment as recorded on the treatment completion page or during follow-up as recorded on the study evaluation completion page or the survival follow-up page).
- Date of progression is the first assessment date at which the overall lesion response was recorded as progressive disease.
- Date of last adequate tumor assessment is the date the last tumor assessment with overall lesion response of CR, PR or SD which was made before an event or a censoring reason occurred. In this case the last tumor evaluation date at that assessment is used. If no post-baseline assessments are available (before an event or a censoring reason occurred) the date of randomization/start of treatment is used.
- Date of next scheduled assessment is the date of the last adequate tumor assessment plus the protocol specified time interval for assessments. This date may be used if back-dating

is considered when the event occurred beyond the acceptable time window for the next tumor assessment as per protocol (see [Section 14.1.3.2.8](#)).

Example (if protocol defined schedule of assessments is 3 months): tumor assessments at baseline - 3 months - 6 months - missing - missing - PD. Date of next scheduled assessment would then correspond to 9 months.

- Date of discontinuation is the date of the end of treatment visit.

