14.1.3.2.9 Sensitivity analyses

This section outlines the possible event and censoring dates for progression, as well as addresses the issues of missing tumor assessments during the study. For instance, if one or more assessment visits are missed prior to the progression event, to what date should the progression event be assigned? And should progression event be ignored if it occurred after a long period of a patient being lost to follow-up? It is important that the protocol and RAP specify the primary analysis in detail with respect to the definition of event and censoring dates and also include a description of one or more sensitivity analyses to be performed.

Based on definitions outlined in [Section 14.1.3.2.7](#), and using the draft FDA guideline on endpoints (Clinical Trial Endpoints for the Approval of Cancer Drugs and Biologics, April 2005) as a reference, the following analyses can be considered:

Table 14-5 Options for event dates used in PFS, TTP, duration of response

Situation		Options for end-date (progression or censoring) ¹ (1) = default unless specified differently in the protocol or RAP	Outcome
A	No baseline assessment	(1) Date of randomization/start of treatment ³	Censored
B	Progression at or before next scheduled assessment	(1) Date of progression (2) Date of next scheduled assessment ²	Progressed Progressed
C1	Progression or death after exactly one missing assessment	(1) Date of progression (or death) (2) Date of next scheduled assessment ²	Progressed Progressed
C2	Progression or death after two or more missing assessments	(1) Date of last adequate assessment ² (2) Date of next scheduled assessment ² (3) Date of progression (or death)	Censored Progressed Progressed
D	No progression	(1) Date of last adequate assessment	Censored
E	Treatment discontinuation due to ‘Disease progression’ without documented progression, i.e. clinical progression based on investigator claim	(1) N/A (2) Date of discontinuation (visit date at which clinical progression was determined)	Ignored Progressed
F	New anticancer therapy given	(1) Date of last adequate assessment (2) Date of secondary anti-cancer therapy (3) Date of secondary anti-cancer therapy (4) N/A	Censored Censored Event Ignored
G	Deaths due to reason other than deterioration of ‘Study indication’	(1) Date of last adequate assessment	Censored (only TTP and duration of response)

¹. =Definitions can be found in [Section 14.1.3.2.7](#)

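### SAP 2.7.3 can censor early unscanned deaths at day 1 in the PFS analysis, and its parenthetical gives the wrong date for a death after a single CR, PR or SD scan

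*SAP*

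**What the plan says.** The PFS paragraph of SAP 2.7.3 has three sentences.

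1. Patients with neither documented progression nor death are censored at their last scan showing non-progression.
2. "Patients without any valid post-baseline tumor assessment response (one of CR, PR, SD, or PD) will be censored on the start date of treatment".
3. Patients whose progression or death comes after two or more consecutive missed assessments "will be censored on the last valid tumor assessment", with a bracketed alternative: "or on the start date of treatment among those with only one valid postbaseline tumor assessment".

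Protocol Appendix 1 sets the reference rules.

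- Section 14.1.3.2.1 defines the PFS event as "first documented progression or death due to any cause" and censors only patients who have had no event.
- Section 14.1.3.2.7 states: "Date of last adequate tumor assessment is the date the last tumor assessment with overall lesion response of CR, PR or SD", made before the event or censoring reason. It adds: "If no post-baseline assessments are available (before an event or a censoring reason occurred) the date of randomization/start of treatment is used".
- In Table 14-5, row C1 ("Progression or death after exactly one missing assessment") is by default an event at its own date. Row C2 ("Progression or death after two or more missing assessments") is by default censored at the last adequate assessment.
- The table header lets the protocol or RAP choose otherwise, and the SAP Introduction counts the SAP among the RAP documents. The text under the table, however, asks for a clear statement of whether and why the default is dropped for situation C.

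**The concern.** The first and third sentences of the SAP paragraph each say whether they concern patients with or without an event. The second does not, and its list of valid responses includes PD, so it can be read as a stand-alone rule that overrides death. On that reading a patient who dies before the first scan leaves the analysis at day 1 instead of counting as an early PFS failure.

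The parenthetical in the third sentence is a separate fault. If a patient has one CR, PR or SD scan, misses two or more, and then dies, that scan is the last valid assessment. The main clause gives its date and the parenthetical gives day 1. The protocol keeps the start date for patients with no post-baseline assessment, not for those with one. The parenthetical therefore discards follow-up during which the patient was known to be progression-free.

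Section 2.7.3 gives no reason for departing from the Table 14-5 defaults, and SAP section 4 does not list 2.7.3 among the changed sections. At stake are the PFS curves, medians and 90% confidence intervals in small groups.

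**Working it through.** The documents state no PFS figure to reproduce, so the rules are applied to test patients and then to a Kaplan-Meier illustration.

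**Inputs.** Cycles are 21 days and scans fall on Day 1 of cycles 3, 5 and 7 (protocol 7.2.1): (3−1)×21+1 = day 43, (5−1)×21+1 = day 85, (7−1)×21+1 = day 127. Phase II groups have 20, 20, 21 and 20 patients (Study Status, Amendment 05). The counts k, m and p below are assumptions.

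**Rules side by side**

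| Patient | Scans missed | SAP, literal | Protocol default |
|---|---|---|---|
| No scan, death day 30 | 0 | Censored day 1 | Event day 30 |
| No scan, death day 60 | 1 | Censored day 1 | Event day 60 |
| No scan, death day 100 | 2 | Censored day 1 | Censored day 1 |
| SD day 43, death day 100 | 1 | Event day 100 | Event day 100 |
| SD day 43, death day 150 | 2 | Main clause: day 43; parenthetical: day 1 | Censored day 43 |
| SD days 43 and 85, death day 200 | 2 | Censored day 85 | Censored day 85 |

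The rules differ only in rows 1, 2 and 5. Row 1 rests on the definition in 14.1.3.2.1; row 2 rests on that definition and row C1. For progressions, the parenthetical conflicts with the main clause only if the late PD scan is not itself counted as valid. A lone late PD goes to the start date under both documents.

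**Part 1: k unscanned deaths before day 43, p progressions at day 43, no other early censoring**

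- Protocol: S(43) = (n − k − p)/n. Literal SAP: S(43) = (n − k − p)/(n − k). The ratio is n/(n − k), whatever p is, and holds from day 43 onward.
- n = 20, k = 1, 2, 3, 4: ratio 1.053, 1.111, 1.176, 1.250.
- n = 21: 1.050, 1.105, 1.167, 1.235.
- n = 20, p = 8: 55.0% becomes 57.9% (k = 1), 50.0% becomes 55.6% (k = 2), 45.0% becomes 52.9% (k = 3), 40.0% becomes 50.0% (k = 4).
- If the one death comes at day 60 after one missed scan (p = 8), the literal curve is first lower and then higher: 11/19 = 57.9% against 12/20 = 60.0% at day 43, and 57.9% against 11/20 = 55.0% from day 60.

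**Part 2: m deaths after one SD scan at day 43 and two missed scans, p progressions at day 43**

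- Protocol: S(43) = (n − p)/n. Parenthetical: S(43) = (n − p − m)/(n − m). The ratio is constant from day 43.

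| n = 20 | Protocol S(43) | m = 1 | m = 2 | m = 3 |
|---|---|---|---|---|
| p = 4 | 80.0% | 78.9% (×0.987) | 77.8% (×0.972) | 76.5% (×0.956) |
| p = 8 | 60.0% | 57.9% (×0.965) | 55.6% (×0.926) | 52.9% (×0.882) |
| p = 12 | 40.0% | 36.8% (×0.921) | 33.3% (×0.833) | 29.4% (×0.735) |

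**Both together, n = 20, p = 8.** Literal (12 − k − m)/(20 − k − m) against protocol (12 − k)/20:

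- k = 2, m = 1: 9/17 = 52.9% against 50.0%.
- k = 2, m = 2: 8/16 = 50.0% against 50.0%.
- k = 1, m = 3: 8/16 = 50.0% against 55.0%.

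**The case against.** The paragraph has a natural order: event-free patients, then the fallback date when they have no scan, then patients with an event. Protocol 14.1.4.5.1 likewise uses the start date only where time is to be censored at the last tumor assessment. On that reading the second sentence restates a convention and part 1 has no effect. This is a fair reading, but nothing in the sentence imposes it. The dataset specifications that might settle it are a separate document, so which derivation was programmed cannot be known here.

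On part 2, a bracketed alternative is an explicit exception, and it is coherent where the one valid assessment is the late PD scan itself. That stands for progressions. It does not rescue a death after one CR, PR or SD scan, where the stated date departs from the C2 default.

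Such patients should be few: an end-of-treatment scan can supply a second assessment, and new therapy leads by default to censoring at the last adequate one. The 9-weekly schedule after treatment also matters. Counted from day 43, the next scans fall on days 43 + 63 = 106 and 106 + 63 = 169, so a death at day 150 would follow only one missed scan and be an event under both documents. This moves the death day needed for the illustration; it does not change the ratios, which depend only on n, p and m.

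Finally, the RAP may depart from the defaults. That is true, but the protocol then asks for the reason, and none is given.

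**Conclusion.** The concern holds, as a minor one. Part 2 is wrong as written: for a death after exactly one CR, PR or SD scan and two or more consecutive missed assessments, the SAP assigns day 1 where the scan date is due. Part 1 is conditional: its effect is zero if the sentence was programmed for event-free patients only. Otherwise it turns early deaths that the protocol counts as events into day-1 censorings. Deaths with no scan after two or more missed assessments are not in dispute.

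The two faults pull in opposite directions. Part 1 raises the curve from the last affected death onward, and part 2 lowers it. The documents do not give the numbers of affected patients, so neither the net direction nor the actual size can be stated. The larger illustrated effects need several affected patients in a group of about 20. ORR and CBR decisions do not use PFS, and OS still counts every death.

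**What to change.** 1. Limit the second PFS sentence of SAP 2.7.3 to patients with neither a valid post-baseline assessment nor a PFS event. Add that a death without any valid post-baseline assessment is an event at the date of death if fewer than two consecutive scheduled assessments were missed before it. Count missed assessments against the patient's actual schedule rather than a fixed day, because scans have a ±1 week window, shift with delayed infusions (protocol 7.1) and become 9-weekly after treatment (7.1.5, 7.2.1).
2. In the third sentence, censor at the last valid CR, PR or SD assessment before the event. Reserve the start date for patients who have no such assessment before the event.
3. If a departure from the Table 14-5 defaults is intended, state it and its reason in the SAP.

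The cost is two SAP sentences and the matching PFS derivation, with no new data. The first change alters nothing if the event-free reading was already programmed; otherwise it lowers PFS from the last affected death onward. The second raises PFS or leaves it unchanged.

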2.8 Safety analyses

The assessment of safety is based on the type and frequency of Adverse Events (AEs) as well as on the number of laboratory values that fall outside of pre-determined ranges (Common Toxicity Criteria for Adverse Events (CTCAE) grading limits or normal ranges as appropriate). Other safety data include electrocardiogram and vital signs.

The safety set will be used for summaries and listings of safety data with the exception of DLTs for which the DDS will be used.

The overall observation period will be divided into three mutually exclusive segments:

1. pre-treatment period: from day of patient's informed consent to the day before first dose of study treatment
2. on-treatment period: from day of first dose of study medication to 30 days after the last dose of study treatment
3. post-treatment period: from 31 days after date of last administration of study treatment

Safety summaries will primarily be based on all data from the on-treatment period. Following last administration of study treatment, adverse events (including serious adverse events), and new antineoplastic therapies are collected for a period of 150 days for PDR001 and 90 days for MCS110. Following start of new antineoplastic therapy, only treatment related adverse events will be collected. Select summaries of related adverse events will be produced for the combined on-treatment and post-treatment periods for patients receiving PDR001 (see [Section 2.8.1](#)).

2.8.1 Adverse events (AEs)

Adverse events will be coded and graded using the latest version of MedDRA and CTCAE, respectively, available at the time of reporting. If CTCAE grading does not exist for an AE, grades 1, 2, 3, or 4 corresponding to the severity of mild, moderate, severe, and life-threatening, respectively, will be used. CTCAE grade 5 (death) will not be used in this study. Death information will be collected on the "Death" eCRF page.

Abnormal laboratory values or test results occurring after informed consent constitute adverse events only if they induce clinical signs or symptoms, are considered clinically significant, require therapy (e.g., hematologic abnormality that requires transfusion or hematological stem cell support), or require changes in study medication(s).

All AEs will be listed. All AE summaries will be summarized (frequency counts and percentages) by system organ class and/or preferred term, and maximum severity grades, unless noted otherwise.

Summary tables for AEs have to include only AEs that started or worsened during the on-treatment period, the treatment-emergent AEs. However, all safety data (including those from the pre and post-treatment periods) will be listed and those collected during the pre-treatment and post-treatment period are to be flagged.

The following AE summaries will be produced:

- AEs regardless of study drug relationship (including CTC grade 3-4)
- AEs suspected to be study drug related (including CTC grade 3-4)
- AEs regardless of study drug relationship leading to discontinuation of study drug
- AEs which are not SAEs regardless of study drug relationship (for CTRD)
- SAEs regardless of study drug relationship

A patient with multiple CTC grades for an AE will be summarized under the maximum CTC grade recorded for the event. A subject with multiple occurrences of an AE is counted only once in the AE category (e.g. system organ class, preferred term).

2.8.1.1 Adverse events of special interest / grouping of AEs

An adverse event of special interest is a grouping of adverse events that are of scientific and medical concern specific to compound PDR001. These groupings are defined using MedDRA terms, SMQs (standardized MedDRA queries), HGLTs (high level group terms), HLT (high level terms) and PTs (preferred terms). Customized SMQs (Novartis MedDRA queries, NMQ) may also be used. A NMQ is a customized group of search terms which defines a medical concept for which there is no official SMQ available or the available SMQ does not completely fit the need. It may include a combination of single terms and/or an existing SMQ, narrow or broad.

For each specified AESI, number and percentage of subjects with at least one event of the AESI occurring during on-treatment period will be summarized.

Summaries of these AESIs will be provided by study treatment.

A listing of all grouping levels down to the MedDRA preferred terms used to define each AESI will be generated.

2.8.2 Deaths

All deaths occurred in the study will be listed with principal cause reported/preferred term and following summaries will be produced:

- All deaths with cause of death by primary system organ class and preferred term

2.8.3 Laboratory data

Laboratory data will be converted into SI units and classified (by Novartis Oncology Statistical Programming) into CTC grades according to CTCAE v4.03 as applicable. Grade 5 will not be used.

Baseline comparisons will be done based on shift tables but not considered for derivation of CTC grade.

Laboratory data for which a CTC grading does not exist will be classified into low, normal, or high based on local laboratory normal ranges as applicable.

The following summaries will be produced for hematology and coagulation, biochemistry, urinalysis parameters:

- For parameters with CTC grades: Shifts from baseline to the worst post-baseline CTC grade,
- For parameters with no CTC grades defined: Shifts from baseline to the worst post-baseline using low/normal/high classifications.

The following listings will be produced:

- Listing of all laboratory data with values flagged to show corresponding CTC grades and the classifications relative to the laboratory reference ranges (i.e., High (H) or Low (L)).

Both fasting glucose and non-fasting glucose will be summarized and listed for information integrity. Both of glucoses will be combined and reported based on CTCAE v4.03. Fasting glucose values will be flagged in the listing.

Table 2-1 and Table 2-2 lists all laboratory parameters that will be summarized.

Table 2-1 Laboratory parameters for which CTCAE grades are defined

Hematology and coagulation		Biochemistry		Urinalysis
White Blood Cells (WBC)	↑↓	Creatinine	↑	Protein ↑
Hemoglobin	↓	Uric acid	↑	
Platelets	↓	Magnesium	↑↓	
Neutrophils(absolute or %)	↓	Calcium	↑↓	
Lymphocytes(absolute or %)	↑↓	Phosphate	↓	
Partial thromboplastin time (PTT)	↑	Albumin	↓	
Activated partial thromboplastin time (APTT)	↑	AST (SGOT)	↑	
International normalized ratio (INR)	↑	ALT (SGPT)	↑	
		Chloride	↓	
		Bicarbonate	↓	
		Total Bilirubin	↑	
		Glucose	↑↓	
		Alkaline Phosphatase	↑	
		Creatine kinase	↑	

↑ Indicates that CTC grade increases as the parameter increases.

↓ Indicates that CTC grade increases as the parameter decreases.

Table 2-2 Laboratory parameters (without CTCAE grades) for which lab reference ranges are defined

Hematology and coagulation	Biochemistry	Urinalysis
Prothrombin time (PT)	Blood Urea Nitrogen (BUN) or Urea	Specific gravity
Hematocrit	T3 [free]	Glucose
Basophils (absolute or %)	T4 [free]	Blood
Eosinophils(absolute or %)	TSH	Bilirubin
Monocytes(absolute or %)	Direct bilirubin	Ketones
	Indirect bilirubin	White Blood Cells
	Lactate dehydrogenase (LDH)	pH

A listing will be produced for the serum pregnancy test and only patients with positive test results will be included.

